1 TITLE PAGE

Study title: A prospective, single arm, open label post market study assessing the safety and efficacy of Nerivio for the treatment of migraine in children under the age of 12

Test Device: Nerivio

Indication studied: Acute treatment of migraine

Study description: Prospective, single arm, open label post market study

Sponsors: Theranica Bioelectronics Ltd

Protocol: RWE-009

Clinical Phase: Post market study

Study period: First user first treatment - May 2020
Last user last treatment - October 2023

Investigators: [name] [name]

Statistician: [name].
Koren Statistics
[name]

2 RWE-009 Study Protocol

Title	A prospective, single arm, open label post market study assessing the safety and efficacy of Nerivio for the treatment of migraine in children under the age of 12
Investigational Device	Nerivio is an FDA-approved remote electrical neuromodulation (REN) device for the acute and/or preventive treatment of migraine with or without aura in patients 12 years of age or older. Nerivio delivers transcutaneous electrical stimulation to the upper arm to induce conditioned pain modulation (CPM) that activates a descending endogenous analgesic mechanism. The treatment is self-administered and controlled by a smartphone application.
Objectives	The study assessed the safety and efficacy of Nerivio for acute treatment of migraine in children under the age of 12.
Participant Population	Children who were prescribed with the Nerivio device for the treatment of migraine and were under the age of 12.
Sample size	The sample size was defined as all Nerivio users in the Nerivio database under the age of 12 in the day of their first treatment
Inclusion Criteria	
• Prescribed with Nerivio device for the treatment of migraine• Age under 12 at their first Nerivio treatment• Treat with Nerivio at least once
Exclusion Criteria	
• Treatments shorter than 30 minutes
Study Design	A prospective, data analysis of users that met the inclusion criteria was performed. All data that were reported prior and following the treatments by the users using the electronic diary within the Nerivio application were downloaded from Theranica server in an unidentified manner.

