Exploratory efficacy endpoints	
Use of migraine medications
 
Treatment patterns of Nerivio use as a standalone treatment vs. in combination with medications were extracted from the 2-hours post-treatment reports, as the percentage of treatments in which no rescue headache medications were used (Nerivio standalone), or Nerivio was used with over-the-counter (OTC) medications, or with prescription medications (Rx).
 
Nerivio treatment stimulation intensity
 
Treatment intensity (stimulation current) is set by patients via the smartphone app and automatically recorded. The average intensity over all treatments per patient was calculated to provide personal intensity levels, which was used for the analyses. Average personal intensity levels and the range for 80% of the users were calculated over the patient cohort.
 
Nerivio utilization
 
Average (and/or median) of number of Nerivio treatments per month. A specific cohort of this outcome considers safety in patients who use the device at high frequency, close to the every-other-day regime of preventive treatment.

Datasets	
1. Intent to treat analysis set (ITT) The ITT analysis set includes all users who had at least one treatment2. Modified intent to treat analysis set (mITT) The mITT analysis set includes all ITT participants who had at least 2 treatments with prospective electronic diary reports at the beginning of the treatment ("baseline") and 2 hours post the beginning of the treatment.
Data Analysis	The ITT analysis set was used for the safety assessments and the mITT analysis set was used for the efficacy assessments.

STATISTICAL CONSIDERATIONS FOR RWE-009 STUDY

The study hypothesis was that treatments of migraine with the Nerivio device in children will be as safe and effective as previously described in adolescents and adults.

DATA COLLECTION

BASELINE DATA

Baseline participant characteristics (age, gender) were collected from the Nerivio account of each participant.

TREATMENT DATA

Treatment data was retrieved from the Nerivio app for each treatment. Data includes automatic parameters (e.g time of treatment, location, device serial number, treatment intensity etc...) and individual information completed by the participant (pain level before and after the treatments, migraine symptoms, functional disability before and after the treatment etc...)

COMPUTER SOFTWARE

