All statistical analyses and data presentations, including tabulations and listings, were performed using the SAS version 9.4 software.

STATISTICAL ANALYSIS

Demographic and Baseline Analysis

Demographic and baseline condition related characteristics will be tabulated and compared between the participant age data type. Continuous variables will be summarized by a mean, standard deviation, minimum, median and maximum and categorical variables by a count and percentage.

Safety Endpoints Analysis

The rate of device related adverse event (DRAE) was calculated ad the number of reported DRAE divided by the number of participants in the study.

Efficacy Endpoints Analysis

All the endpoints will be calculated for Qualified Attacks only, Qualifies treatement was defined as

- 1 - Attacks treated with Nerivio for at least 30 minutes
- 2 – Pre and post treatment data was reported by the participant for the specific treatment
- 3 – No rescue medications were taken before and during the 2 hours post treatment, according to the participant report

Consistent efficacy was conducted in cases where at least two qualified treatments were performed. Patients who experienced the outcome (e.g., pain freedom) in at least 50% of their reported treatments, during which they did not report the use of rescue medications, were considered responders.

Headache pain and functional disability were rated at baseline and at 2 h post-treatment on a 4-point scale: severe, moderate, mild, or none. Migraine associated symptoms (photophobia, phonophobia, and nausea/vomiting) were marked as present or not.

Pain relief was calculated as a decrease from severe or moderate levels at baseline to mild or none at 2 h posttreatment.

Functional disability relief was calculated as any improvement in disability from baseline to 2 h posttreatment.

Pain/functional disability freedom was calculated as a decrease from any pain/disability level at baseline to none at 2 h post-treatment.

Freedom from a specific migraine-associated symptom was calculated as the percentage of patients reporting the presence of that symptom at baseline and the lack of that symptom at 2 h post-treatment. Freedom from at least one associated symptom was calculated as the percentage of patients in which one or more associated symptom(s) were reported at baseline and the lack of at least one of those symptoms at 2 h post-treatment.

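### The only hypothesis compares children with unspecified earlier results in older users, and no older group is planned, so a match or gap cannot be put down to age.

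*Combined protocol and SAP*

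**What the plan says.** The hypothesis under Statistical Considerations for RWE-009 Study is comparative: "treatments of migraine with the Nerivio device in children will be as safe and effective as previously described in adolescents and adults". The documents give no reference rate, publication, endpoint definition, calendar period, analysis set, margin or test for what was previously described.

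The title describes a "prospective, single arm, open label post market study". The inclusion criterion in the RWE-009 Study Protocol table is "Age under 12 at their first Nerivio treatment", and the sample size is "all Nerivio users in the Nerivio database under the age of 12 in the day of their first treatment". The same table gives the approved use as "for the acute and/or preventive treatment of migraine with or without aura in patients 12 years of age or older" and adds: "The treatment is self-administered and controlled by a smartphone application". The title page dates the children's data from May 2020 to October 2023.

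Efficacy Endpoints Analysis counts only treatments of 30 minutes or more, with reports before and after, and without rescue medication. A child needs two or more such treatments and is a responder if the outcome occurs in half or more of them. Safety is the device-related adverse event (DRAE) rate in the ITT set. No safety or efficacy analysis includes an older group. The only mention of a comparison by age, under Demographic and Baseline Analysis, concerns baseline characteristics, which "will be tabulated and compared between the participant age data type".

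**The concern.** The hypothesis needs two quantities, and the plan defines only one. The child rate is built by a detailed set of rules on treatment length, reporting, rescue use, number of treatments and the 50% threshold. The quantity on the other side is left to whatever earlier figure is chosen when the results are written up. If that figure rests on a single treatment, a different rescue rule, another period or a different reporting filter, those features are mixed with age and the plan offers no way to separate them.

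A margin or a confidence interval around the child rate would not solve this. Both deal with imprecision, whereas the question here is whether the two rates measure the same thing. At stake is the comparative conclusion. The child rates themselves remain usable as description.

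**Working it through.** The plan states no figure to reproduce: there is no reference rate, margin, power or test. The check has two parts.

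**1. What is fixed on each side of the comparison**

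| Feature | Children under 12 | Earlier adolescent and adult results |
|---|---|---|
| Source | The Nerivio database | Not named |
| Period | May 2020 to October 2023 | Not given |
| Treatments counted | 30 minutes or more, both reports, no rescue | Not given |
| Patients counted | Two or more qualified treatments | Not given |
| Response | Outcome in half or more of treatments | Not given |
| Safety measure | DRAE rate, ITT set | Not given |

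The safety measure is itself stated in two ways. The primary endpoint is the percentage of patients reporting DRAEs, while Safety Endpoints Analysis divides the number of DRAEs by the number of participants. The two differ once any child reports more than one event, so an earlier figure could correspond to one and not the other.

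**2. How far the responder rule alone can move an efficacy rate**

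Assumptions, none from the documents: each treatment succeeds independently with the same probability p at every age, and a patient has n counted treatments. The chance of being a responder is P(X ≥ n/2), with X binomial(n, p). The number of successes needed is n/2 rounded up: 1 of 2, 2 of 3, 2 of 4, 3 of 5.

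Worked for p = 0.4:
- n = 2: 1 − 0.6² = 0.640
- n = 3: 3 × 0.4² × 0.6 + 0.4³ = 0.288 + 0.064 = 0.352
- n = 4: 1 − 0.6⁴ − 4 × 0.4 × 0.6³ = 1 − 0.1296 − 0.3456 = 0.525
- n = 5: 10 × 0.4³ × 0.6² + 5 × 0.4⁴ × 0.6 + 0.4⁵ = 0.2304 + 0.0768 + 0.0102 = 0.317

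| p (single-treatment rate) | n = 2 | n = 3 | n = 4 | n = 5 |
|---|---|---|---|---|
| 0.5 | 75% | 50% | 69% | 50% |
| 0.4 | 64% | 35% | 52% | 32% |

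At p = 0.5, against a single-treatment rate of 50%, the rule adds 25 points at n = 2 and 19 at n = 4, and nothing at n = 3 or n = 5. At p = 0.4, against 40%, it adds 24 points at n = 2 and 12 at n = 4, but takes off 5 at n = 3 and 8 at n = 5. With more treatments at p = 0.4 it gives 37% at n = 10 and 25% at n = 20. Neither the size nor the sign is constant.

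Independence is not essential. With an assumed within-patient correlation of 0.3 and n = 2, the responder rate is 1 − (q² + 0.3pq), where q = 1 − p. This is 1 − (0.25 + 0.075) = 0.675 at p = 0.5 and 1 − (0.36 + 0.072) = 0.568 at p = 0.4, still about 17 points above the single-treatment rate.

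Two consequences follow. A different response rule can produce a large apparent age difference where there is none. Even under the same rule, a different number of treatments per patient can do so: at p = 0.4, n = 2 and n = 5 differ by 64.0 − 31.7 = 32.3 points.

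**The case against.** The strongest reply is that the study is descriptive. Its objective is to assess safety and efficacy in children, it is openly single arm, and no test against older users is planned, so no planned estimate is biased. On that view the weakness is one framing sentence, curable by naming the reference and its definitions or by dropping the comparison. This stands in part: the child rates are unaffected, and restricting the conclusion is a legitimate way out. But the sentence is the plan's only hypothesis, and while it remains it needs a comparator.

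Several stronger readings are tempting and are not supported:

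- A reader might infer that the earlier rates were built differently from the child rates. The documents do not identify those results, which could have used the same rule and the same app.
- A reader might infer that the responder rule flatters children. The table shows no gap or a reversal at odd numbers of treatments, and a single-treatment historical rate is only an assumption.
- A reader might carry the efficacy illustration over to safety. The responder rule and the two-treatment requirement do not touch the primary endpoint, and no distortion of the DRAE rate has been shown. The safety comparison shares only the lack of a defined comparator.
- A reader might take the age wording under Demographic and Baseline Analysis as a planned comparison with older users. It is unclear, covers baseline characteristics only, and could mean age bands within the under-12s.

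It is also true that an older cohort from the same database would not remove all selection. Under-12 use lies outside the approved age range, and prescribing and reporting may differ by age.

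**Conclusion.** The point holds in a limited form. The plan does not show that its comparator is comparable, and it includes no older group that could make it so. An apparent match or gap with earlier results therefore cannot be attributed to age rather than to definition, period or selection. Whether such differences exist is unknown from the documents.

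The possible size concerns the secondary efficacy endpoints. Under the stated assumptions, rule and number of treatments alone give responder rates from 32% to 64% when per-treatment success is 40%, and from 50% to 75% when it is 50%, for 2 to 5 treatments per patient. These are illustrations, not estimates of bias in this study.

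That the database holds users aged 12 or older is an inference, but a strong one: an under-12 filter is applied to the database of a device approved from age 12. The change should be made if the comparative claim is to be kept, because a better comparator appears to be at hand.

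**What to change.** 1. Run the same extraction for users aged 12-17 and for adults at first treatment, over May 2020 to October 2023.
2. Apply identical ITT, mITT, qualified-treatment, responder and DRAE rules to all three age groups, after settling which DRAE measure is meant.
3. Show the age groups side by side, with differences and 95% intervals. Make the unweighted comparison the main one.
4. Show results by number of qualified treatments and by baseline pain level as a sensitivity analysis only. The number of qualified treatments may itself depend on response, so conditioning on it in the main analysis could introduce bias.
5. Base the comparative statement on this concurrent comparison and quote earlier published rates only as context. If the comparison is not run, limit the conclusion to descriptive rates in children.

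The cost is the same program run on two more age strata, and extra tables. No new enrolment is needed if, as inferred, the older users are already in the database. Identical rules and dates remove differences of definition and period but not all selection, so the report must state the residual selection, including that under-12 use is outside the approved age range. A margin for what counts as equally safe and effective is a separate matter. It becomes interpretable only once the comparator is defined.

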Primary endpoint - Safety	Rate of Device Related Adverse Events Incidence of device-related adverse events (DRAEs) reported by subjects. a) Percentage of patients reporting DRAEs b) Severity of reported DRAEs

Secondary endpoints - efficacy	
Consistent Headache Relief at 2 Hours Post-treatment.
 
The proportion of subjects reporting headache relief at 2 hours post-treatment in at least 50% of all their treatments.
 
Consistent Freedom from Headache at 2 Hours Post-treatment.
 
The proportion of subjects reporting freedom from headache at 2 hours post-treatment in at least 50% of all their treatments.
 
Freedom from a specific migraine associated symptom.
 
Freedom from a specific migraine associated symptom was calculated as the percent of patients reporting the presence of that symptom at baseline, and the lack of that symptom at 2-hours post-treatment in at least 50% of all their treatments.
 
Per the ICHD-3, migraine associated symptoms are:
 
a) Hyper sensitivity to light (phonophobia)b) Hyper sensitivity to sound (phonophobia)c) Nausea (with or without vomiting) 
Functional disability relief
 
Functional disability relief was calculated as decrease of at least one level of functional disability from baseline to 2-hours post-treatment in at least 50% of all their treatments.
 
Disability levels are (0) none (full function), (1) mild disability, (2) moderate disability, and (3) severe disability.
 
Freedom from functional disability
 
Freedom from functional disability was calculated as decrease from any disability level (3, 2, or 1) at baseline to no disability (i.e., return to full function) at 2-hours post-treatment in at least 50% of all their treatments.

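### The single-arm plan hypothesises that the device is as safe and effective in children as in older patients, but gives no reference rate, margin, test, decision rule or measure of precision to judge that by

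*Combined protocol and SAP*

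**What the plan says.** All references are to the combined protocol and SAP.

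- **Hypothesis** (Statistical Considerations for RWE-009 Study): treatment in children "will be as safe and effective as previously described in adolescents and adults". No adolescent or adult rate is given.
- **Design and size** (title page; Sample size row): single arm, open label. "The sample size was defined as all Nerivio users in the Nerivio database under the age of 12" on the day of first treatment. No number and no precision target is stated.
- **Efficacy endpoints** (Secondary endpoints row): responder proportions, for example "The proportion of subjects reporting headache relief at 2 hours post-treatment in at least 50% of all their treatments". The row lists seven rates: headache relief, headache freedom, freedom from each of three symptoms, disability relief and disability freedom. Efficacy Endpoints Analysis adds freedom from at least one symptom.
- **Safety endpoint** (Primary endpoint row; Safety Endpoints Analysis): the share of patients with a DRAE, and severity. The analysis text divides the count of DRAEs by the number of participants.
- **Summary rule** (Demographic and Baseline Analysis): "categorical variables by a count and percentage", with no interval.
- **Who is analysed**: mITT, the efficacy set, requires "at least 2 treatments with prospective electronic diary reports" at baseline and 2 hours. Efficacy Endpoints Analysis then says "Consistent efficacy was conducted in cases where at least two qualified treatments were performed". One condition for a qualified treatment is "No rescue medications were taken before and during the 2 hours post treatment".

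**The concern.** The hypothesis is comparative, but nothing in the analysis sections connects a result to it. A percentage near some earlier adolescent or adult figure could be presented as confirmation even when the data are also compatible with a clearly lower rate. A percentage some way below could be dismissed just as freely. The safety half has the same gap, and safety is the primary endpoint: few or no DRAEs in a small cohort is weak evidence of equal safety unless an upper limit is shown.

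A reader could compute an interval from each endpoint's denominator, but the plan does not require that denominator to be reported. Nor can it be read off the mITT size, because the rates rest on a narrower group that differs by endpoint.

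**Working it through.** **1. Search for a decision rule.** The plan has no figure to reproduce. The candidates that might have served as a rule are:

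| Candidate | Where | What it does |
|---|---|---|
| 50% threshold | Secondary endpoints; Efficacy Endpoints Analysis | Classes one child as a responder; not a benchmark for the cohort rate |
| Comparison by age data type | Demographic and Baseline Analysis | Covers demographic and baseline data only; no test named |
| Count and percentage | Demographic and Baseline Analysis | Describes baseline variables; no interval |
| Sample size statement | Sample size row | Takes all eligible users; no precision basis |

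None links an efficacy or DRAE rate to adolescents or adults. No redaction or missing table appears where such a rule could have stood.

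**2. How imprecise could a responder rate be?** All inputs are assumed: 30, 50, 100 or 200 children, and an observed rate of 60% or 30%. For x responders among n, the exact (Clopper-Pearson) limits are: lower = the 0.025 quantile of Beta(x, n−x+1); upper = the 0.975 quantile of Beta(x+1, n−x).

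| n | Observed 60% | 95% CI | Observed 30% | 95% CI |
|---|---|---|---|---|
| 30 | 18/30 | 41–77% | 9/30 | 15–49% |
| 50 | 30/50 | 45–74% | 15/50 | 18–45% |
| 100 | 60/100 | 50–70% | 30/100 | 21–40% |
| 200 | 120/200 | 53–67% | 60/200 | 24–37% |

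**3. Could a bare percentage mislead?** Suppose the benchmark is 60%, the children's true rate is 50%, and a reader accepts any observed rate of at least 55% as a match. Benchmark, shortfall and reading rule are all assumed. The chance of a match is P(X ≥ 0.55n), with X binomial(n, 0.5):

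- n = 30: P(X ≥ 17) = 0.292
- n = 50: P(X ≥ 28) = 0.240
- n = 100: P(X ≥ 55) = 0.184
- n = 200: P(X ≥ 110) = 0.089

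With a 30% benchmark and a true rate of 20%, the chances are 0.239, 0.186, 0.131 and 0.049.

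**4. Safety.** If no child reports a DRAE, the exact two-sided 95% upper limit is 1 − 0.025^(1/n). For n = 30 this is 1 − 0.025^(1/30) = 0.116; for n = 200 it is 1 − 0.025^(1/200) = 0.018. Under these assumed sizes, the same observed 0% is compatible with a true rate of up to about 12% or up to about 2%.

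**5. Denominators.** mITT needs two reported treatments; the consistent-efficacy rates need two qualified ones, and rescue use disqualifies a treatment. Take a child with exactly two reported treatments and assume a share q of treatments does not qualify. The chance of having fewer than two qualified lies between q (both treatments share the same status) and 1 − (1 − q)² (independent). For q = 0.2 that is 0.20 to 1 − 0.64 = 0.36. Usable counts also differ by endpoint: "Pain relief was calculated as a decrease from severe or moderate levels at baseline", and symptom freedom starts from the symptom being present.

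**The case against.** The best defence is that this is a descriptive post-market study. The Objectives row is not comparative, efficacy is secondary, and there is no success rule to misapply. A descriptive single-arm study may properly omit a test. That stands, and it is why the remedy is estimation and not a non-inferiority test. It does not excuse stating a comparative hypothesis with nothing to judge it by.

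A second objection is that every size above is assumed. That also stands: the calculations show possible imprecision, not a demonstrated error, and the 5-point reading rule in step 3 is illustrative.

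Four stronger readings are tempting, and the documents do not support them:

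- *The plan names summary statistics only for demographics.* It names proportions for efficacy, and percentages, averages, a median and a range for the exploratory endpoints. What it lacks is a measure of precision.
- *Children with fewer than two qualified treatments are counted in the responder rates.* Efficacy Endpoints Analysis keeps them out. What remains is that mITT is wider than the group analysed, and the difference is not reported.
- *The rule that one success in two treatments is enough distorts the rates.* The rule is openly stated. Comparing assumed mixes of mostly low and mostly high treatment counts, the responder rate moves by 1 to 5 points in eight of nine scenarios and by 11 in one, with no fixed direction. Rates split by treatment count would be a preference, not a needed correction.
- *A formal benchmark test should be added.* Seven listed rates against two older groups would make up to 7 × 2 = 14 comparisons with no rule across them. With a true rate and benchmark of 60% and a 10-point margin, a rule requiring the lower 95% limit to exceed 50% would be met with chance 18%, 24%, 46% and 79% at 30, 50, 100 and 200 children (all assumed).

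**Conclusion.** The point holds for both halves of the hypothesis. That no reference rate, margin, test, decision rule or interval is given is a matter of reading and rests on no assumption. Its size does rest on assumptions, because the documents give no cohort size, rate or benchmark. Over 30 to 200 children, the 95% interval around an observed 60% has a half-width of about 18 points, (77.3 − 40.6)/2, falling to about 7, (66.8 − 52.9)/2. A true 10-point shortfall from a 60% benchmark would pass as a near match with chance 29% falling to 9%.

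A reader might infer that the device works less well in children, or that the reported rates will be wrong. Neither follows. The percentages can be computed correctly; they cannot by themselves settle the stated hypothesis. The change should be made, but it concerns reporting and wording, not the validity of the data.

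**What to change.** 1. In Efficacy Endpoints Analysis, require the numerator, denominator and a 95% confidence interval (exact or Wilson) for every responder rate. Do the same in Safety Endpoints Analysis for the share of patients with at least one DRAE. These binomial intervals suit a count of patients, not the events-per-participant ratio now described there.
2. In Statistical Considerations, restate the hypothesis as an aim to estimate safety and responder rates in children under 12. Keep the present sentence on record. The title page gives October 2023 for the last treatment, so label the restatement and the added intervals post hoc if made after that. Describe any comparison with earlier adolescent or adult figures as descriptive only.
3. For each efficacy endpoint, add one line giving the number of mITT children in the denominator and the number excluded for having fewer than two usable qualified treatments.

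**Cost:** a few sentences and table rows from data already held. Intervals may be wide, and the study gives up a formal claim that the device is as safe and effective in children as in older patients. The 50% responder rule can stay as it is.

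### The only safety formula counts device-related adverse event reports per participant, whereas the primary endpoint is the share of children who report one

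*Combined protocol and SAP*

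**What the plan says.** The protocol table, under Primary endpoint - Safety, heads the endpoint as a rate of device-related adverse events (DRAEs) and gives it two components: a) "Percentage of patients reporting DRAEs" and b) "Severity of reported DRAEs".

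In the statistical part, Safety Endpoints Analysis is a single sentence. It defines the DRAE rate as "the number of reported DRAE divided by the number of participants in the study". No other safety formula appears, and nothing there summarises severity.

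Three other places bear on the point:

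- **Data Analysis** fixes the population: "The ITT analysis set was used for the safety assessments". The ITT set is every user with one or more treatments.
- **Nerivio utilization**, among the exploratory endpoints, mentions a cohort that "considers safety in patients who use the device at high frequency, close to the every-other-day regime of preventive treatment", but gives no safety formula for it.
- **Efficacy Endpoints Analysis** shows how the plan writes when the child is the unit: "percentage of patients in which one or more associated symptom(s) were reported at baseline".

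**The concern.** The endpoint's numerator is children; the formula's numerator is reports. Children treat repeatedly, some close to every other day, so one child can report several DRAEs. Nothing says that such a child is counted once.

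At stake is the meaning of the primary result. The stated hypothesis is that treatment in children is as safe as previously described in older users. Even a purely descriptive comparison of that kind needs to know whether a figure refers to patients or to reports. Given only the ratio, a reader cannot recover the share of children affected.

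**Working it through.** The plan states no sample size, DRAE count or expected DRAE rate, so there is no figure of its own to reproduce. The check compares the two definitions and then illustrates the gap on assumed counts.

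**Definitions**

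- E = number of DRAE reports
- K = number of distinct children with at least one DRAE
- N = number of children in the ITT set
- m = E/K, the mean number of reports per affected child

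Component a) is K/N. The formula in Safety Endpoints Analysis, read literally, is E/N.

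**Relation.** E/N = (K/N) × m. Since m is at least 1, E/N is never below K/N when both use the same reports and the same N. They are equal only when m = 1. For a given E of at least 1 and no larger than N, K can be any whole number from 1 to E, so one ratio is compatible with any share of children from 1/N up to E/N.

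**Fixed number of reports (E = 6 assumed, N assumed)**

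| N | Formula E/N | K/N if K = 6 (m = 1) | K/N if K = 3 (m = 2) | K/N if K = 1 (m = 6) |
|---|---|---|---|---|
| 100 | 6.0% | 6.0% | 3.0% | 1.0% |
| 200 | 3.0% | 3.0% | 1.5% | 0.5% |
| 300 | 2.0% | 2.0% | 1.0% | 0.33% |

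**Fixed number of children (N = 100 and K = 3 assumed).** The share affected is 3.0%. The formula gives 3.0%, 6.0% or 12.0% if each of the three children reports 1, 2 or 4 DRAEs.

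**No clustering within children.** Suppose every treatment carries the same DRAE probability q, independently, and each child has t treatments. The formula then has expectation t × q, and the share affected is 1 − (1 − q)^t.

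| t | q | Reports per child | Share of children affected |
|---|---|---|---|
| 5 | 0.01 | 0.050 | 4.9% |
| 20 | 0.02 | 0.400 | 33.2% |
| 50 | 0.02 | 1.000 | 63.6% |

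Likewise, 6 reports falling at random on 200 children reach on average 200 × (1 − (199/200)^6) = 5.93 children, or 2.96% against a ratio of 3.0%. The gap is therefore negligible when DRAEs are rare and do not cluster. It grows with frequent use, and it grows when the same children report repeatedly.

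**The case against.** The strongest reply is that component a) is already fully defined: the endpoint row gives the numerator and Data Analysis gives the ITT denominator. On that view the sentence under Safety Endpoints Analysis is either loose wording or a deliberate event rate, which would suit the endpoint's heading. The plan's use of patient-level wording elsewhere could even suggest that the choice of reports was intended. The ratio is never called a percentage of patients. Large gaps need clustering, which nothing in the documents demonstrates, and any error would make the device look less safe.

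Much of this stands. The wording may be loose, the gap may be zero, the counts above are assumed, and the direction is conservative. The direction also holds only if both quantities use the same children and the same reports.

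The conflict nevertheless remains. The endpoint row uses the rate heading for an endpoint whose first component is a patient percentage, and the analysis section gives a quantity of the same name a different numerator. An analyst who follows the analysis section literally will not produce component a), and the plan nowhere says that the ratio is an additional measure.

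**Conclusion.** The concern holds. As written, the only safety formula does not compute component a) of the primary endpoint unless every affected child reports exactly one DRAE. Component b) has no stated summary.

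The textual mismatch is certain; its numerical effect is unknown because the documents give neither N nor DRAE counts. The inflation factor is m, the mean number of reports per affected child: no effect at m = 1, a doubling at m = 2. This assumes a common denominator and common capture of DRAEs. No hypothesis test, margin or decision rule depends on the figure, so the consequence is limited to the unit and interpretation of the primary safety result. It should be corrected because it concerns the primary endpoint and the correction is small.

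**What to change.** Replace the sentence under Safety Endpoints Analysis with a child-level definition: distinct ITT children with at least one DRAE, divided by all ITT children. Then:

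- Report the number of DRAEs separately, under its own label.
- For component b), tabulate the reported DRAEs by severity. Worst severity per child is a useful addition.
- Use the same child-level count in the high-frequency cohort.
- If the ratio has already been calculated as written, keep it, labelled as DRAE reports per participant, and record the clarification with its date.

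The cost is a few sentences and, at most, a re-count of reports by child. That re-count needs DRAE reports that can be linked to a child. Treatments must already be linkable, because the consistency endpoints group them by child. The documents do not say whether this extends to DRAE reports: data were "downloaded from Theranica server in an unidentified manner", and the open-ended list under Treatment Data, "individual information completed by the participant (pain level before and after the treatments, migraine symptoms, functional disability before and after the treatment" and so on, does not name adverse events. If the reports cannot be linked, the plan should say so and present the ratio only as reports per participant, not as a percentage of patients.
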